### 2.3.5.1 RMST

*Stata: strmst2:*

RMST and curves are estimable using strmst2 (Cronin 2016) in Stata

Will perform conventional RMST analysis:

Requires "stset" as preliminary command.

Strmst2 treat, tau(50) (will not allow factors), where "tau" is the largest time of observation and should be the minimum (by group) of the maximum follow up time (within group).

Observation time starts at the time of the first dose of vaccine and ends on April 30, of the season year or when the child received the second does, whichever was earlier.

For this study, we pre-specify several values of tau:

- (i) 42 – the number of days within which children should receive the second dose
- (ii) 60 days
- (iii) 90 days

Adjustment for covariates using strmst2pw

Robust confidence intervals.

This approach has no support for robust confidence intervals (or for strata). For that reason, we will check all confidence bounds by using bootstrap percentile methods, with 999 resamples at the site level (code will be developed for Stata).

Note: Alternative RMST code available from Royston (2015) using Stata's code strmst. This will be a backup in the event that Cronin's code fails.

## 2.4 Tertiary analysis: Variation across practice sites - descriptive

We anticipate that the effect of the intervention could vary across practice sites.

### 2.4.1 Binary outcomes

#### 2.4.1.1 Mixed effects models

To assess this potential for variation in effect across the intervention sites, we will consider generalized linear mixed effects models (logistic regression with random intercepts and slopes) to mimic the analysis that would occur in a meta-analysis in which variation across sites is expected. The advantage of this approach is that once the random slopes (treatment effects estimating the departure of each site from average) are estimated, we can identify the sites that have either high or low treatment effects. Individual site estimates are shrunk toward the overall average in these methods to avoid problems of unstable site-specific estimates and to reduce the problem of multiple comparisons. This method will, however, allow us to identify the sites with the greatest and least improvements. Once identified, we will attempt to characterize these sites and contact them to discover the possible barriers to improvement.

If mixed effects models reveal no variation of intervention effect across sites, when that result will be reported and this analysis will stop.

Generalized linear mixed effects models. Stata melogit for binary outcomes:

Random intercept (and slopes) for each site (assuming correlated intercept/slope)

Overall test for variation across sites in treatment effect

Likelihood ratio test of random slopes

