## Flu2Text: A Multi-Site Study assessing an Intervention for 2nd Dose of Influenza Vaccine

### Overview of the study

This study will assess the impact of text message reminders on the receipt of the second dose of influenza vaccine and will take place in 40-50 practices over two influenza seasons.

This study includes a sample of up to 4,000 parents over the course of two flu seasons (up to approximately 40-250 parents any of 40-50 sites per influenza season). Eligible parents will have a child who received their first vaccine dose and are in need of 2 doses that season. The study will include parents who have a 6-month through 8-year-old child (or a child who is of the age that necessitates 2 doses, should age recommendations change as determined by the CDC) who received their first vaccine dose and is in need of 2 doses that season. Current recommendations require 2 doses for certain children 6 months through 8 years old.

Within each practice site, parents will be randomized to receive either:

- 1) a series of text message reminders embedded with influenza vaccine health-literacy promoting information, or
- 2) usual care

- *Season 1 (2017-2018):* usual care alone
- *Season 2 (2018-2019):* usual care plus a text message containing a link to health and parenting information from the American Academy of Pediatrics website

The primary outcome will be receipt of two doses of influenza vaccine by the end of the season (April 30). A secondary outcome will be timeliness of receipt of 2nd dose.

The study will be conducted over the 1st season (September 2017–April 2018) as an effectiveness trial and the 2nd season (July 2018–April 2019) as a replication study to validate the approach and allow refinement based on parent and practice feedback. The intervention targets the parent-child dyad.

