## **Study procedures**

### **Practice inclusion criteria:**

- Ability to recruit a minimum of 40 English or Spanish speaking parents per season
- Ability to check the office medical records and/or the city/state immunization information system of the child of the participating parent to confirm dates of first and second influenza vaccination and related visit dates in each season (and ability to provide these dates to the study team)

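### The site-variation analysis stops on a finding of no variation without saying what counts as one; if a non-significant likelihood ratio test is the trigger, small-to-moderate site variation would usually be reported as none

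*Combined protocol and SAP*

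**What the plan says.** Section 2.4 of the SAP is headed "Tertiary analysis: Variation across practice sites - descriptive" and opens with an expectation: "We anticipate that the effect of the intervention could vary across practice sites". Section 2.4.1.1 fits a logistic mixed model, specified as "Random intercept (and slopes) for each site (assuming correlated intercept/slope"), and lists an overall test of variation in treatment effect, named as "Likelihood ratio test of random slopes". The site estimates are to be used to find the sites with the greatest and least improvement, describe them, and contact them about barriers.

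A stop rule precedes this list: "If mixed effects models reveal no variation of intervention effect across sites, when that result will be reported and this analysis will stop". No alpha, reference distribution or interval for the slope variance is given.

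Four other places bear on the point:

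- The opening of the SAP avoids declarations of statistical significance and makes point estimates and confidence bounds the main form of reporting.
- Section 2.1.2.1 acknowledges that the Mantel-Haenszel analysis ignores the effect of between-site variation on the variance, and refers to section 2.4.
- Section 2.4.2 says it applies the same approach to time to vaccination, and there it does speak of testing whether the variation is significant.
- Section 2.0.1 analyses the two seasons separately and combines them only as a secondary analysis.

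**The concern.** Failing to reject zero variance is not evidence that the variance is zero. With some 40 to 50 children per site per season, a site's treatment effect is poorly estimated, so a test of whether those effects differ has little power unless they differ a great deal. The test is also conservative if read against an ordinary chi-square distribution. The null puts the slope variance on the edge of its range, and because intercept and slope are correlated the test removes two parameters, the variance and the covariance.

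Two things are at stake. A report of no variation would end the planned work on high- and low-effect sites, in a trial that expects such sites may exist. It could also be taken as clearing the fixed-effects limitation that section 2.1.2.1 passes to section 2.4.

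**Working it through.** The documents state no power, alpha or detectable variation for this test, so there is no figure of the plan's to reproduce.

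**Inputs from the documents.** The Overview says the study "will take place in 40-50 practices over two influenza seasons" and "This study includes a sample of up to 4,000 parents over the course of two flu seasons". The practice criteria require "Ability to recruit a minimum of 40 English or Spanish speaking parents per season". These agree: 50 sites × 40 × 2 seasons = 4,000. At the cap, 40 to 50 sites average 50 down to 40 children per season; 45 sites give 4,000 / (45 × 2) = 44. Allocation is 1:1 within site. The Background gives second-dose completion of 40-60%; 50% is used.

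**Assumptions not in the documents.** Alpha 0.05; mean log odds ratio 0.3 (50% to 57.4%, about 7 points); SD of site intercepts 0.5; intercept-slope correlation 0; SD of site log odds ratios (tau) from 0 to 0.7.

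**Precision of one site's effect.** With 22 children per arm, the variance of a site's log odds ratio is v = 4 / (44 × 0.25) = 0.364, so its standard error is 0.60. That is twice a tau of 0.3.

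**Power of the listed test.** Logistic mixed models were simulated (500 trials per setting, Monte Carlo standard error up to about 2.2 points). The random-intercept model was compared with the correlated intercept-and-slope model at 45 sites × 44 children. A separate approximate rerun of the same two-parameter test is shown alongside. The last column is the normal probability below -0.3/tau.

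| tau (logit) | SD of site effects, points | Rejected, naive chi-square(2) | Rejected, approximate rerun | Not rejected, naive | Rejected, 50:50 mixture | Sites with effect below zero |
|---|---|---|---|---|---|---|
| 0.2 | 5 | 5% | 5% | 95% | 6% | 7% |
| 0.3 | 7 | 13% | 16% | 84-87% | 17% | 16% |
| 0.4 | 9 | 34% | 43% | 57-66% | 41% | 23% |
| 0.5 | 12 | 69% | 73% | 27-31% | 76% | 27% |
| 0.7 | 16 | 96% | – | 4% | 98% | 33% |

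At tau = 0 the naive reference rejected in 2.0% of trials against a nominal 5%, and the mixture in 3.2%. From tau 0.2 to 0.7 the mixture adds about 1 to 7 points of power.

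**What the SDs mean.** Around a mean effect of about 7 points, tau 0.3 puts 95% of sites between -7 and +21 points, and tau 0.4 between -12 and +25.

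**Sensitivity (naive reference).**

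- At tau 0.5, power is 51% for 40 sites × 40, 65% for 50 × 40, and 61% for 45 sites of unequal size.
- At tau 0.3 it is 13%, 14% and 16% in those same settings. It is also 13% with control log odds 0.8 (69% completion), intercept SD 0.7 and correlation -0.5.
- With both seasons pooled as 45 sites × 88, it is 40% at tau 0.3 and 96% at tau 0.5.

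**Cross-check with a different test.** Cochran's Q has power P(chi-square with K-1 df > c / (1 + tau²/v)). For K = 45, c = 60.48. At tau 0.3, 60.48 / (1 + 0.09/0.364) = 48.5, giving 30%; tau 0.4, 0.5 and 0.7 give 56%, 80% and 99%. Q is more favourable than the listed test but shows the same pattern. Sections 2.0.1 and 4.0 treat each site-season as its own stratum. If the mixed model did so too, pooling would give 90 clusters of 44 rather than 45 of 88. At tau 0.3, Q then has c = 112.02, 112.02 / 1.2475 = 89.8 on 89 df, and power 46% instead of 62%.

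**The case against.** The best reply is that the SAP never says a non-significant test triggers the stop. It says the models must reveal no variation, and its opening section turns away from significance language. A slope variance estimated at or near zero would also fit, and stopping is then natural because the shrunken site estimates nearly coincide. This stands in part: the trigger is inferred. The inference is reasonable, since the likelihood ratio test is the only criterion listed and section 2.4.2 describes the same approach in terms of significance. A stop rule with no criterion needs repair under either reading.

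A reader might go further and infer that large differences between practices would usually be declared absent. The calculations do not support that. SDs of 12 and 16 points are detected in roughly 50-70% and 96% of single-season trials, and 12 points in about 96% with seasons pooled as 45 sites.

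Nor do the documents say that a null result here validates the Mantel-Haenszel interval; section 2.1.2.1 discloses the limitation openly. False reassurance is a risk in how the report is read, not a step in the plan.

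Finally, little site-level learning is lost when variation is small. The reliability of a single site's effect is tau²/(tau² + v): 0.04/0.404 = 10% at tau 0.2 and 0.09/0.454 = 20% at tau 0.3. Ranking sites would then mostly follow noise. That is correct and belongs in the report, but it argues for showing the uncertainty, not for stating that there is no variation.

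**Conclusion.** The concern holds for small-to-moderate variation. The firm part needs no simulation: the rule has no stated criterion, and it would report an absence of variation where the SAP's own reporting policy calls for an estimate and an interval. The conditional part is that, if non-rejection at 0.05 is the trigger, site-effect SDs of about 5 to 9 points would more often than not be reported as none in a single season. At 7 points or more, such an SD is at least as large as the assumed mean effect.

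The 9-point case is the least secure, with non-rejection in about 55-65% of trials under the listed test and 44% under Cochran's Q. All the percentages depend on the assumed alpha, mean effect and intercept SD, and the documents give no expected size for the variation. Because the analysis is tertiary and descriptive, and no primary or secondary estimate rests on it, this is a modest wording repair.

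**What to change.** In section 2.4.1.1:

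- Delete the stop rule.
- Whatever the test shows, report the slope SD with its confidence interval, the implied 95% range of site effects in percentage points, and the shrunken site estimates, with a note that these are imprecise when the SD is small.
- Do not describe a non-rejection as no variation; say what range of SDs the data are compatible with.
- If a p-value is given, refer it to the 50:50 mixture of chi-square(1) and chi-square(2). This is a minor correction and does not cure the low power.

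The cost is a few sentences of SAP text and some further output from a model already planned. No new data are needed, and the primary analysis does not change.

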### 2.4.2 Time to event outcomes – variation across sites

We will use the same approach for time to vaccination, with mixed effects models and letting site be a random effect. In other words, we allow estimated time to vaccination vary by site, and test whether this variation is significant.

Statistical significance of the random site effect can be tested using likelihood ratio statistics.

Stata: mestreg –

```
mestreg treat covariates || site:, distribution(weibull) int(12)
```

```
predict resite, reffects
```

In this example, the variable "resite" will contain the value for the "prediction" at the site level. The prediction will then represent the site-level time to event, and by ordering the sites by this value, we can determine which sites fared best and which fared worst.

R: coxme

Alternative but similar approaches are now in R (Therneau 2018) for the Cox model

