#### **2.1.2.1 Relative risks**

Stratified (by site and language) Mantel Haensel

Estimates = RR and confidence interval

Make a new variable that is the combination of site and language = l\_site

Stata: cs outcome treatment, by(l\_site)

This is a "fixed effects" analysis and does not consider the effect on variance of variation across sites in the effect of treatment (See section 2.4).

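### SAP 2.4.2 fits, tests and ranks only a random site intercept, so it cannot separate how fast sites are from how much the text-message effect varies between sites

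*Combined protocol and SAP*

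**What the plan says.** Section 2.4 opens with its question: "We anticipate that the effect of the intervention could vary across practice sites". Section 2.1.2.1 had already pointed there, noting that the fixed-effects relative risk "does not consider the effect on variance of variation across sites in the effect of treatment (See section 2.4").

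For binary outcomes, 2.4.1.1 specifies a logistic mixed model with correlated random intercepts and slopes by site and a likelihood-ratio test of the slopes. The slopes are what it interprets: "once the random slopes (treatment effects estimating the departure of each site from average) are estimated, we can identify the sites" with high or low treatment effects.

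For time to event, 2.4.2 begins: "We will use the same approach for time to vaccination, with mixed effects models and letting site be a random effect". It then restates the aim: "In other words, we allow estimated time to vaccination vary by site, and test whether this variation is significant". On testing it says: "Statistical significance of the random site effect can be tested using likelihood ratio statistics". The code is "mestreg treat covariates || site:, distribution(weibull) int(12"). One predicted value per site is saved and read as that site's time to event, and "by ordering the sites by this value, we can determine which sites fared best and which fared worst". R's coxme is named as an alternative, without a model formula.

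**The concern.** The likelihood-ratio test and the ranking in 2.4.2 concern a different quantity from those in 2.4.1.1. A random intercept describes how quickly a site's children complete the second dose, whichever arm they are in. Sites can differ in speed for reasons unrelated to the texts: under Parent randomization, usual care is whatever the practice already does, including other reminders, and 3.0.1 lists walk-in versus appointment scheduling as a site characteristic.

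Followed as written, 2.4.2 leaves the question of section 2.4 unanswered for the time-to-event outcome. A reader could take a positive test as evidence that the text effect varies, or take the sites that did best as those where the texts worked. Section 2.4.1.1 attaches actions to its result: stop if the effect does not vary, otherwise characterise and contact the extreme sites. If these carry over to 2.4.2, they would rest on the wrong quantity.

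**Working it through.** **Side by side**

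| Element | 2.4.1.1 (binary) | 2.4.2 (time to event) |
|---|---|---|
| Random part | intercept and treatment slope, correlated | intercept only; nothing follows `site:` |
| Treatment | fixed mean plus site departure | fixed only |
| Likelihood-ratio test | random slopes | random site effect |
| Quantity ranked | site treatment effects | site time to event |

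Prose, test, code and ranking in 2.4.2 all agree with each other, so this is not a slip in one line of code. The documents give no figure to reproduce here.

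**What the intercept measures**

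Let site *j* have log-hazard departure *u* in usual care and *u + v* in the text arm, where *v* is the departure of its text effect from the mean. With 1:1 allocation and treatment fixed, the predicted intercept follows roughly *u + v/2*. It responds to both *u* and *v* and cannot tell them apart.

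Let σ = SD(*u*), τ = SD(*v*), with *u* and *v* independent, and *d* events per site. The correlation with the true *v* is approximately:

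- written ranking: (τ/2) / √(σ² + τ²/4 + 1/*d*)
- slope ranking: τ / √(τ² + 4/*d*)

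**Inputs**

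- Site size: up to 4,000 parents over two seasons and 40–50 practices (Overview), with seasons analysed separately (2.0.1). 4,000 / 2 / 45 ≈ 44 per site, taking all 45 sites as active in the season.
- Completion: 49–50% in usual care and 55–56% with texts in the simulation; the Background gives 40–60%. So *d* ≈ 44 × 0.525 ≈ 23.
- Assumed, not in the documents: σ and τ, mean log hazard ratio 0.2, Weibull shape 1.2, follow-up uniform over 60–210 days, 5% test level.

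For σ = τ = 0.3:

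- written: 0.15 / √(0.09 + 0.0225 + 0.0435) = 0.38
- slope: 0.3 / √(0.09 + 0.174) = 0.58

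**Simulation** (200 trials per setting, Monte Carlo SE up to 3.5 points; intercept test against ½χ²₁, slope test against a 50:50 mixture of χ²₁ and χ²₂)

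| What varies between sites | Written test rejects | Slope test rejects |
|---|---|---|
| Nothing | 3.5% | 2.5% |
| Baseline speed only, SD 0.2 / 0.3 | 90% / 100% | 2% / 2% |
| Effect, SD 0.3 / 0.5, equal control-arm speed | 59% / 99% | 73% / 100% |
| Effect, SD 0.3 / 0.5, equal text-arm speed | 49% / 98% | 70% / 100% |
| Effect, SD 0.3 / 0.5, equal site averages | 3% / 2% | 49% / 96% |

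The last row is a bounding case: *u* = −*v*/2 makes *u + v/2* zero, so the written test has nothing to find.

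Spearman correlation of each ranking with the true site text effect, *u* and *v* independent:

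| σ / τ | Written | Slope |
|---|---|---|
| 0.3 / 0.3 | 0.40 | 0.58 |
| 0.3 / 0.5 | 0.56 | 0.76 |
| 0.5 / 0.3 | 0.26 | 0.50 |
| 0.5 / 0.5 | 0.43 | 0.75 |

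The formulas above give 0.38, 0.57, 0.27 and 0.42 for the written ranking, and 0.58, 0.77, 0.58 and 0.77 for the slope ranking. These are close, although the third slope value is optimistic.

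**Sensitivity**

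- 25 sites of 80: baseline SD 0.2 only, 90% (written) against 4% (slope); ranking at 0.3/0.3, 0.40 against 0.65.
- 45 uneven sites, about 1,980 children: 92% against 2%; ranking 0.35 against 0.53.
- A separate simulation used 50 sites of 40, exponential times and SD 0.5. Completion was 78–81%, higher than the Background suggests. The written test rejected in 100% of trials whether only speed or only the effect varied; the slope test rejected in 3.5% and 100%. With both varying, the predicted intercept correlated 0.43 with the true effect.

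**The case against.** Section 2.4 is labelled tertiary and descriptive, and 2.4.1.1 already covers the binary outcome, including the primary endpoint. Section 2.4.2 states openly that it lets time to vaccination vary, and it does not call its ranking a treatment effect. The claim of sameness could mean only that a mixed model with a random site effect is used. The code is partly illustrative, and the pointer in 2.1.2.1 concerns the relative risk, which 2.4.1.1 serves. On the low-stakes status this is right. On the reading, if only speed was meant, the linking sentence is wrong and the section's opening question goes unanswered for this outcome, so the text needs changing either way.

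The heterogeneity used is also large. With mean log hazard ratio 0.2, SDs of 0.3 and 0.5 imply that the texts slow vaccination in Φ(−0.2/0.3) = 25% and Φ(−0.2/0.5) = 34% of sites. A two-stage approximation at smaller effect SDs (45 sites, about 23 events each, baseline SD 0.3) gives:

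| Effect SD | Slope test rejects | Slope ranking | Written ranking |
|---|---|---|---|
| 0.10 | 7% | 0.22 | 0.12 |
| 0.15 | 13% | 0.32 | 0.18 |
| 0.20 | 21% | 0.41 | 0.25 |

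This stands as a limit on the gain. If true variation is small, both rankings are weak and the slope test has little power. The slope remains the better guide and the only one aimed at the stated question. The cases with equal text-arm speed or equal site averages need baseline and effect to be perfectly negatively related, so they show bounds, not expectations.

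**Conclusion.** The concern holds. The mismatch follows from the text alone and needs no simulation: 2.4.2 has no site-by-treatment term, and the coxme line does not supply one. The accurate statement is that the analysis cannot separate speed from effect variation. It would be wrong to say it cannot detect effect variation, because the intercept absorbs part of it.

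The size depends on assumed site SDs. The finding that pure speed differences trigger the written test and leave the slope test near or below its nominal level held across site numbers and for uneven site sizes. The gain in ranking is moderate at SDs of 0.3 to 0.5 and small below that. The consequence is confined to one tertiary, descriptive analysis.

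**What to change.** In 2.4.2, add a random treatment slope by site, correlated with the intercept: `|| site: treat, covariance(unstructured)` in mestreg, or `(1 + treat | site)` in coxme. Test the slope variance against the intercept-only model, using a reference distribution that allows for the variance boundary, and rank sites on the predicted slope, as 2.4.1.1 does. Reword the two sentences on what varies and what is tested. Keep the intercept test and ranking only if they are labelled as site speed.

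The cost is one model term and a few words, with no new data. The model may fail to converge, and site slopes will be imprecise at about 44 children per site, so shrinkage will be heavy. The slope is on a log-hazard-ratio scale, which 2.3 and 2.3.5 otherwise avoid, though the existing Weibull and coxme plan already implies it.

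A smaller change is to drop the claim of sameness and state that 2.4.2 describes site differences in time to vaccination only. That removes the contradiction but leaves the question of section 2.4 unanswered for this outcome, and the SAP should then say so.

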### Background

Influenza, as evidenced by seasonal epidemics, remains a significant and largely preventable source of morbidity and mortality resulting in an estimated 31 million outpatient visits, 226,000 hospitalizations, and 3,000 to 49,000 deaths annually (depending on the virulence of the circulating strain), along with a high cost burden from direct medical expenses and days lost from work. Young children, the focus of this proposal, are at especially high risk for hospitalization and serious influenza complications including pneumonia and neurological outcomes like seizures and encephalopathy. They are also a source of transmission to other high-risk household members. However, influenza vaccine coverage is low. Only 58.9% of U.S. children 6 months to 17 years-old receive at least one needed influenza dose annually. Young children <9 years are at particular risk for under vaccination because they require 2 doses at least 4 weeks apart in the first influenza season they are vaccinated, since one dose does not confer adequate influenza protection; some previously vaccinated children also require 2 doses in subsequent seasons depending on their previous influenza vaccinations. Even among those who need two doses in a given season and who receive the first dose, only 40-60% receive the second dose.

Timeliness is also key, as children are not fully protected until two weeks after receiving the second dose, many children do not receive this second dose close to 4 weeks after the first, as recommended. This delay leaves many children unprotected when influenza virus begins circulating. Increasing timely receipt of second doses is also a worthwhile focus as parents (meaning the adult in a parenting role, including guardians) have already “accepted” vaccination as evidenced by their child receiving the first dose.

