#### ***Study Intervention: Text Messages***

Messages will be sent in English or Spanish based on parent preference.

Using date of initial vaccine as day 0, text messages will be sent to all parents randomized to the intervention on the following days:

- Day 14: notifying parents that their child is in need of a second flu shot.
- Day 21: educational text messages, with interactivity, through which parents can select to receive more information via text message.
- Day 25: letting parents know when and where they will need to go to receive the second shot
- Day 28 (day vaccine is due): it is now time to take [child] to be vaccinated (2nd flu shot).
- Day 42 (2 weeks after it is due): another interactive message will assess potential vaccine barriers and offer selected responses.

Texts will stop after day 42. We will not be able to know from the practices in time to stop messages after a child was vaccinated. However, as the shot is not due until day 28, it would likely only be the day 42 message that could come after the child was vaccinated. That message has been worded to first assess whether the child received the vaccine.

**Dates of influenza vaccinations and related visit dates:** Dates of influenza vaccinations and related visit dates will be collected from the practices. The part of the Patient Enrollment/Outcomes Forms that stays with the site will have child's first and last name and date of birth. The site will use this to identify the medical record, extract relevant influenza vaccination dates and related visit dates and transfer this information to the research team. Practices will do this by using their medical records and/or by checking their city or state immunization registry should the practice have no record of receipt of subsequent influenza doses for the current season.

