### 2.2. Continuous outcomes (if any) – not applicable

**We have none. This section is not developed.**

### **2.3 Secondary analysis: Time to event (Aim 2)**

As a secondary outcome, and to confirm that statistical significance from our primary analysis applies equally to time to event data, we will use stratified (by practice site) time-to-event analysis for receipt of vaccine.

Our goal will be to use, where possible, assumption free methods and avoid parametric approaches, and at the same time to present results in a format that can be interpreted easily to a clinical audience. For these reasons, we are deliberately avoiding traditional approaches such as Cox regression and common metrics such as hazard ratios.

This section covers two separate topics:

First, in keeping with our goal of using assumption-free, randomization-test based methods, we shall apply this approach to time-to-event analyses.

Second, we shall estimate restricted mean survival times to arrive at more meaningful estimate of time to event and to avoid "hazard ratios"

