#### **2.3.1 Time zero**

Time zero for all time to event analyses is the date of child's initial vaccine dose.

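### SAP 2.4.2: the Weibull random-intercept model makes the test for site variation in time to vaccination too liberal, and it omits the treatment slope that section 2.4 calls for

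*Combined protocol and SAP*

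**What the plan says.** SAP section 2.4, headed as tertiary and descriptive, states its purpose: "We anticipate that the effect of the intervention could vary across practice sites". For the binary outcome, section 2.4.1.1 uses a mixed logistic model with random intercepts and slopes by site, and tests the slopes by likelihood ratio. Section 2.4.2 says that time to vaccination will be handled the same way. The command it gives is "mestreg treat covariates || site:, distribution(weibull) int(12". The random site effect is to be tested by likelihood ratio, and the predicted site effects are to be sorted to show which sites did best and worst. A Cox mixed model (coxme) is mentioned as a similar alternative, with no rule for when it replaces the Weibull. The covariates are not listed and no check of fit is planned.

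Other parts of the documents fix the shape of these data. SAP section 2.3.1: "Time zero for all time to event analyses is the date of child's initial vaccine dose". Protocol, Background: "they require 2 doses at least 4 weeks apart in the first influenza season they are vaccinated", and of those who start, "only 40-60% receive the second dose". Protocol, Text Messages section: "as the shot is not due until day 28". SAP section 2.3.5.1 ends observation on April 30 whatever the enrolment date. For the Aim 2 comparison, section 2.3 sets the goal to "use, where possible, assumption free methods and avoid parametric approaches".

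**The concern.** There are two separate problems.

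First, a Weibull hazard can only rise, stay level or fall over the whole period from day 0. The hazard here is close to zero for four weeks, peaks once the dose is due, and then drops towards zero because about half of the children never return. When a model misses the time course this badly, residuals are larger than it expects, and a random site effect can absorb the excess. Time after the peak adds exposure with few events, so sites with shorter follow-up may also look faster. At stake are a significance test that reports site variation too readily, and a site ordering that partly reflects when each site enrolled.

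Second, the command contains only a random intercept. It asks whether sites differ in overall speed, with both arms shifted alike. That is not the question section 2.4 poses, which is whether the effect of the texts differs by site.

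**Working it through.** The documents give no error rate or power for this analysis, so there is no stated figure to reproduce.

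**Inputs from the documents.** Time zero is the first dose; the second is due from day 28; completion is 40-60%; censoring is at April 30; 84-90% of children have a 90-day window (SAP 2.3.5; simulated 88%); 40-50 practices (45 used); at least 40 parents per practice per season; up to 4,000 over two seasons. The simulated season has 45 × 44 = 1,980 children, against 4,000 / 2 = 2,000.

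**Assumed, not in the documents.** The dose-time curve after day 28, the spread of mean enrolment date between sites, and a 5% test level.

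**Step 1. Model.** For site j, h(t) = λ p t^(p−1) exp(β·treat + u_j), with u_j ~ N(0, σ²). It rises if p > 1, is flat if p = 1 and falls if p < 1. It cannot be zero, then peak, then fall.

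**Step 2. Null simulation (σ = 0).** Doses were given at 28 days plus a lognormal gap (median day 42, log-SD 0.9), with a plateau at 40%, 50% or 60% in usual care and 4 points higher with texts. The Weibull model was fitted with 12-point adaptive quadrature. Because σ² = 0 is on the boundary, the critical value is 2.71: 0.5 × P(χ²₁ > 2.71) = 0.5 × 0.10 = 0.05. The comparator was the same random intercept on a piecewise-constant baseline from day 28, standing in for the Cox mixed model. There were 200 runs per row (100 where starred). The Monte Carlo error at a 30% rate is √(0.30 × 0.70 / 200) = 0.032. Correlations are between predicted site effect and mean site enrolment date.

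| Completion | Children per site | Enrolment SD between sites (days) | Weibull rejects | Flexible rejects | Correlation, Weibull | Correlation, flexible |
|---|---|---|---|---|---|---|
| 40% | 44 | 0 | 14% | 1% | +0.12 | +0.01 |
| 50% | 44 | 0 | 21.5% | 3% | +0.13 | +0.02 |
| 60% | 44 | 0 | 30% | 4.5% | +0.14 | +0.02 |
| 60% | 60* | 0 | 42% | 3% | +0.12 | 0.00 |
| 60% | 44 | 15 | 39.5% | 3.5% | +0.21 | +0.01 |
| 60% | 44 | 30 | 63% | 5.5% | +0.36 | −0.01 |
| 60% | 44* | 45 | 90% | 1% | +0.59 | +0.04 |
| 60%, season covariate | 44 | 30 | 30% | 5.5% | +0.05 | −0.01 |

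With data generated from a true Weibull, the same code rejected in 2-3%, so the inflation comes from misfit. With the plateau present, squared residuals were 1.17-1.33 times what the Weibull implies. The spurious site SD had a median of 0.09-0.18 on the log-hazard scale, a hazard ratio per SD of exp(0.09) = 1.09 to exp(0.18) = 1.20. With the 28-day delay but no plateau, rejection was 8.5% (shared calendar) and 12.5% (SD 30), so the plateau does most of the damage.

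**Step 3. Other assumptions.** A second simulation (45 × 45; completion 45%/52%; gap 28 + exponential with mean 25 days; follow-up mean 150 days, within-site SD 45) rejected in 22% with a shared calendar and in 29%, 40% and 54% at between-site SD 15, 25 and 35 days. Its non-parametric baseline rejected in 2.5-4%. A further null run (45 × 44, 120 runs per setting) gave 14% with a shared calendar and 31% at SD 25, against about 2%.

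**Step 4. Ranking when sites truly differ.** The Step 3 curve was used with 44 children per site and an assumed true site SD. The table shows the Spearman correlation with the true ranking.

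| True site SD (log-hazard) | Weibull, calendar SD 0 / 15 / 35 days | Non-parametric baseline |
|---|---|---|
| 0.2 | 0.63 / 0.63 / 0.60 | 0.63 |
| 0.3 | 0.77 / 0.77 / 0.74 | 0.77 |
| 0.4 | 0.85 / 0.85 / 0.82 | 0.85 |

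The largest loss is 0.77 − 0.74 = 0.03 (the same in each row).

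**Step 5. Missing slope.** Under the coded model the treatment hazard ratio at site j is exp(β + u_j) / exp(u_j) = exp(β), identical at every site. The predicted site value therefore holds no information on how the intervention effect varies. Section 2.4.1.1 has the slope; section 2.4.2 claims the same method and leaves it out.

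**The case against.** The strongest case against runs as follows. The section is tertiary and descriptive, and section 2.4.1 already examines treatment-effect variation for the primary outcome. The inflated test matters only if sites do not differ; where they do, Step 4 shows little loss, and at true site SD 0.3-0.4 both methods always detected variation. The covariates are left open, and season of first dose is already a candidate factor (SAP 3.0.1.1). Section 2.4.2 presents its code as an example, names coxme, and describes its target as letting time to vaccination vary by site.

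Much of this stands, and it limits the point. A season covariate largely removes the calendar correlation (+0.36 to +0.05 at SD 30), but the false-positive rate is still 30%. Naming coxme without saying which model governs does not protect the test. Describing the target as overall site speed confirms the departure from section 2.4 and does not cure it.

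A reader might also infer that section 2.4.2 contradicts section 2.3. The documents do not support that: section 2.3 is qualified by its words on feasibility and governs the Aim 2 treatment comparison, while 2.4 is a separate section. The tension is worth a sentence of justification in the SAP, no more.

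One limit applies to the remedy. Neither coxme itself nor any random treatment slope was fitted; the comparators were other flexible baselines.

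**Conclusion.** The point holds as an inflated error rate plus a missing term. With no true site difference, a shared enrolment calendar and 44-45 children per site, the planned test rejects in about 14-30% of seasons at a nominal 5%, against about 1-6% with a flexible baseline. Larger sites, or enrolment dates that differ between sites, push it higher. These figures rest on the assumed dose-time curve and the 5% level; the higher ones also rest on an assumed enrolment spread of 15-45 days. The direction was the same under two different dose-time curves.

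Two stronger readings are tempting and should be resisted. One is that the model will find site differences that do not exist: the figures show a raised chance, and in most shared-calendar seasons at this site size the test did not reject. The other is that the ranking mainly reflects the enrolment calendar: without an assumed spread the correlation is only 0.12-0.14, and the loss is at most 0.03 when sites truly differ.

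The slope omission needs no simulation and follows from the text. Neither part affects a primary or secondary estimate.

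**What to change.** In section 2.4.2, make the Cox mixed model already named there (coxme), or another flexible baseline starting at day 28, the stated method for both the site-variation test and the site predictions. List the covariates, and consider including season of first dose.

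Add a random treatment slope, `(1 + treat | site)`, and test that slope to address variation in the intervention effect. Report site slopes as shrunken descriptive estimates only: at the minimum of 40 per site and 1:1 allocation there are 40 / 2 = 20 children per arm, and the reliability of ranking on slopes has not been evaluated.

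The cost is small. It takes a few lines of text, no new data, and software the section already cites. The one downside is descriptive use of a Cox baseline, which section 2.3 sets aside for the Aim 2 comparison; one sentence should explain why it is acceptable here.
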